- *Secondary outcome 2: PPM within 48 hours following PCI or hospital discharge, whichever comes first*
- *Secondary outcome 3: uTVR within 48 hours following PCI or hospital discharge, whichever comes first*
- *Secondary outcome 4: death within 48 hours following PCI or hospital discharge, whichever comes first*
- *Secondary outcome 5: death, PPM, uTVR or major bleeding within 48 hours following PCI or hospital discharge, whichever comes first, where PPM is defined as at least one troponin elevation of ≥ 10 times the upper limit of normal and at least 20% of greater than the baseline troponin value, per the troponin Local Laboratory within 48 hours following PCI or hospital discharge, whichever comes first (a non-inferiority margin of 12.4% will be used for the short tirofiban versus eptifibatide comparison)*
- *Secondary outcome 6: at least one troponin elevation of ≥ 10 times the upper limit of normal and at least 20% of greater than the baseline troponin value, per the troponin Local Laboratory, within 48 hours following PCI or hospital discharge, whichever comes first (a noninferiority margin of 12.4% will be used for the short tirofiban versus eptifibatide comparison)*
- *Secondary outcome 7: at least one troponin elevation of ≥ 20 times the upper limit of normal and at least 20% of greater than the baseline troponin value, per the troponin Local Laboratory, within 48 hours following PCI or hospital discharge, whichever comes first*
- *Secondary outcome 8: at least one troponin elevation of ≥ 50 times the upper limit of normal and at least 20% of greater than the baseline troponin value, per the troponin Local Laboratory, within 48 hours following PCI or hospital discharge, whichever comes first*

Note: This table will also be repeated for Per-Protocol Population.

Table 18. Summary of Incidence of Adverse Events by Treatment Group – Safety Population

Parameter	Short Tirofiban (N=)			Eptifibatide (N=)			Long Tirofiban (N=)		
	N of Events	N of Subjects	% of Subjects	N of Events	N of Subjects	% of Patients	N of Events	N of Subjects	% of Subjects
Is it a Serious Adverse Event?									
Yes									
No									
If yes, serious indicator									
Death									
Life-threatening									
Required/prolonged hospitalization									
Significant/permanent disability									
Medically significant									
Is this event ongoing?									
Yes									
No									
Severity of adverse event									
Mild									
Moderate									
Severe									
Relationship to study drug									
Probably related									
Possibly related									
Unlikely related									

Parameter	Short Tirofiban (N=)			Eptifibatide (N=)			Long Tirofiban (N=)		
	N of Events	N of Subjects	% of Subjects	N of Events	N of Subjects	% of Patients	N of Events	N of Subjects	% of Subjects
Action taken to the study drug									
None									
Discontinued									
Outcome									
Recovered									
Recovered with sequelae									
Unresolved									
Death									
Unknown									

The percentage is based on the number of serious adverse events.

Note: A patient may have reported more than one adverse event. Percentages based on the total number of safety population patients in each treatment group.

Note: This table will also be repeated for Serious Adverse Events.

Table 19. Incidence of Adverse Events by System Organ Class (SOC) and Preferred Term (PT) by Treatment Group – Safety Population

System Organ Class (SOC) Preferred Term (PT)	Short Tirofiban (N=)		Eptifibatide (N=)		Long Tirofiban (N=)	
	Event	Subject (%)	Event	Subject (%)	Event	Subject (%)
TOTAL (ALL SOC/PT)						
SOC 1						
PT 1.1						
PT 1.2						
SOC 2						
PT 2.1						
PT 2.2						

Note: Adverse Events will be coded by MedDRA version x. A patient may have reported more than one adverse event. Percentages based on the total number of safety population patients in each treatment group.

Note: This table will also be repeated for Serious Adverse Events.

Table 20. Descriptive Statistics of Safety Outcomes by Treatment Group – Safety Population

Parameter	Treatment Group		
	Short Tirofiban (N=)	Short Tirofiban (N=)	Short Tirofiban (N=)
REPLACE-2 major bleeding, n (%)			
Yes			
No			
TIMI major bleeding, n (%)			
Yes			
No			
REPLACE-2 minor bleeding, n (%)			
Yes			
No			
TIMI minor bleeding, n (%)			
Yes			
No			
REPLACE-2 plus major bleeding, n (%)			
Yes			
No			
TIMI plus major bleeding, n (%)			
Yes			
No			
Sum of REPLACE-2 major and minor bleeding, n (%)			
Yes			
No			

Parameter	Treatment Group		
	Short Tirofiban (N=)	Short Tirofiban (N=)	Short Tirofiban (N=)
Sum of REPLACE-2 plus major and minor bleeding, n (%)			
Yes			
No			
Sum of TIMI major and minor bleeding, n (%)			
Yes			
No			
Sum of TIMI plus major and minor bleeding, n (%)			
Yes			
No			
Non-bleeding adverse event, n (%)			
Yes			
No			
Thrombocytopenia (< 100,000 cells/ μ L), n (%)			
Yes			
No			
Severe thrombocytopenia (< 50,000 cells/ μ L), n (%)			
Yes			
No			
Profound thrombocytopenia (< 20,000 cells/ μ L), n (%)			
Yes			
No			
Length of hospital stay (hours)			

RESPONSIVE
RELIABLE
RESULTS

SAVI-PCI
Statistical Analysis Plan
Version FINAL
20 February, 2019
Page 77 of 79

Parameter	Treatment Group		
	Short Tirofiban (N=)	Short Tirofiban (N=)	Short Tirofiban (N=)
Available n			
Mean \pm SD			
95% CI for Mean			
Median (IQR)			
Min - Max			

Table 21. Fisher’s Exact Test for Binary Safety Outcomes – Safety Population

Statistic	Level	DF	Value	p-value
Fisher’ exact test	Short Tirofiban vs. Eptifibatide			
Fisher’ exact test	Short Tirofiban vs. Long Tirofiban			
Fisher’ exact test	Long Tirofiban vs. Eptifibatide			

Note: p-value is based on the Fisher’s mid-p test.

Note: The Binary Safety Outcomes are the following:

- *Bleeding events according to REPLACE-2 Major bleeding definition*
- *Bleeding events according to TIMI Major bleeding definition*
- *Bleeding events according to REPLACE-2 Minor bleeding definition*
- *Bleeding events according to TIMI Minor bleeding definition*
- *Bleeding events according to REPLACE-2 Plus Major bleeding definition*
- *Bleeding events according to TIMI Plus Major bleeding definition*
- *Sum of REPLACE-2 Major and Minor bleeding*
- *Sum of REPLACE-2 Plus Major and Minor bleeding*
- *Sum of TIMI Major and Minor bleeding*
- *Sum of TIMI Plus Major and Minor bleeding*
- *Non-bleeding adverse events*
- *Thrombocytopenia (< 100,000 cells/ μ L)*
- *Severe Thrombocytopenia (< 50,000 cells/ μ L)*
- *Profound Thrombocytopenia (< 20,000 cells/ μ L)*

Table 22. Student t-Test for Quantitative Safety Outcome – Safety Population

Statistic	Level	DF	t Value	p-value
t-test	Short Tirofiban vs. Eptifibatide			
t-test	Short Tirofiban vs. Long Tirofiban			
t-test	Long Tirofiban vs. Eptifibatide			

Note: p-value is based on the Student t-test.

Note: The Quantitative Safety Outcome is the length of hospital stay.

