5.2.3 Timing of Oral Antiplatelet Therapy, PCI & Study Drug Administration

PCI will be performed according to institutional guidelines and standards. The index PCI procedure will be completed as clinically appropriate. Any PCI device approved by the FDA may be used (investigational stents may not be used in this study).

All clinical events from the time of study drug administration will be recorded. The number and position of coronary stents placed as well as the outcome of the procedure will be recorded.

All patients must receive aspirin (81 - 325 mg daily is recommended) and oral P2Y₁₂ antagonist therapy throughout the course of the study.

Patients who are on a P2Y₁₂ antagonist at time of randomization should remain on that same P2Y₁₂ agent post-randomization.

Patients who have not received any oral P2Y₁₂ antagonist therapy within 24 hours prior to randomization must receive a loading dose between randomization and 15 minutes after completion of the PCI (defined as final removal of the guiding catheter), preferably as close to time of randomization as possible.

Recommended loading doses for the oral P2Y₁₂ antagonist therapies are the following: clopidogrel 600 mg; prasugrel 60 mg; and ticagrelor 180 mg.

Patients will be administered unfractionated heparin as an initial I.V. bolus of 50 U/kg prior to PCI. Additional heparin boluses will be administered according to the suggested guidelines in Appendix 4.

Study drug will be prepared and labeled accordingly for each patient as described in the pharmacy manual. Tirofiban will be provided by Sponsor and packaged in 100 mL bags/vials containing 5.0 mg of tirofiban. Eptifibatide will be provided by the Institution and packaged in 10 mL bolus vials containing 20 mg eptifibatide and 100 mL infusion vials containing 75 mg of eptifibatide. See Pharmacy Manual for details of study drug preparation.

Patients assigned to short tirofiban will receive a 25 µg/kg bolus administered by I.V. push followed by a 0.15 µg/kg/min infusion for the duration of the PCI procedure plus a minimum of one hour and up to a maximum of two hours post-PCI. Sites have the option of administering the tirofiban 25 µg/kg bolus via I.V. pump over approximately 3 minutes or

bolus push with syringe. Sponsor will supply T-ports (Trudell Medical Marketing) to use for filling syringe for bolus administration.

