9.3.4 Potential Covariates and/or Subgroups

- Patient with acute coronary syndromes
- STEMI > 48 hours
- Stable angina
- Troponin baseline negative
- Troponin baseline positive
- Femoral access PCI
- Radial access PCI
- Total stent length
- Use of a closure device
- Number of stents implanted
- Single vessel
- Multivessel
- Number of vessels treated
- Total infusion time

- Patients receiving P2Y₁₂ antagonist therapy between 24 and 6 hours prior to randomization
- Patients receiving P2Y₁₂ antagonist therapy between 6 and 1 hours prior to randomization
- Patients receiving P2Y₁₂ antagonist therapy between 1 hour prior to randomization and 15 minutes after completion of the PCI procedure
- Type 1 diabetes mellitus
- Type 2 diabetes mellitus
- Prior use of GPIIb/IIIa inhibitor therapy
- Indication for PCI
- Age < 65 years, ≥65 years and ≥75 years
- Sex
- Race
- Clopidogrel
- Prasugrel
- Ticagrelor
- Elective PCI
- Urgent PCI

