3.10.4 Potential Covariates and/or Subgroups

As an exploratory analysis, appropriate univariate statistics will be used to identify potential confounders for inclusion in multivariable regression models for assessment of the primary endpoint. The following covariates will be considered:

- Patient with acute coronary syndromes (defined as any previous diagnosis of unstable angina, NSTEMI or STEMI)
- STEMI > 48 hours
- Stable angina
- Baseline troponin (positive vs. negative)
- Planned PCI access (femoral vs. radial)
- Number of stents implanted
- Number of vessels treated (multivessel vs. single vessel)
- Total infusion time
- Patients receiving P2Y12 antagonist therapy between 24 and 6 hours prior to randomization
- Patients receiving P2Y12 antagonist therapy between 6 and 1 hours prior to randomization
- Patients receiving P2Y12 antagonist therapy between 1 hour prior to randomization and 15 minutes after completion of the PCI procedure
- Type 2 diabetes mellitus
- Age < 65 years, ≥ 65-74 years and ≥ 75 years
- Sex
- Clopidogrel
- Prasugrel
- Ticagrelor
- Indication for PCI (Urgent vs. Elective)

RESPONSIVE
RELIABLE
RESULTS

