Femoral			
Radial			
Number of stents implanted			

Parameter	Treatment Group		
	Short Tirofiban (N=)	Eptifibatide (N=)	Long Tirofiban (N=)
Available n			
Mean ± SD			
95% CI for Mean			
Median (IQR)			
Min - Max			
Vessel involvement, n (%) ²			
Single Vessel			
Multivessel			
Patients receiving P2Y12 antagonist therapy between 24 and 6 hours prior to randomization, n (%)			
Yes			
No			
Patients receiving P2Y12 antagonist therapy between 6 and 1 hours prior to randomization, n (%)			
Yes			
No			
Patients receiving P2Y12 antagonist therapy between 1 hour prior to randomization and 15 minutes after completion of the PCI procedure, n (%)			
Yes			
No			
Type 2 diabetes mellitus, n (%)			
Yes			
No			
Indication for PCI, n (%)			

Parameter	Treatment Group		
	Short Tirofiban (N=)	Eptifibatide (N=)	Long Tirofiban (N=)
Elective			
Urgent			

¹ Defined as any previous diagnosis of unstable angina, NSTEMI or STEMI

² Ascertained by 'Number if stents implanted' indicated on the Procedure Report Form; ≥ 1 implanted stent = multivessel

Note: This table will also be repeated for Per-Protocol Population.

Table 14. Descriptive Statistics of Primary Outcome by Treatment Group – mITT Population

Parameter	Treatment Group		
	Short Tirofiban (N=)	Eptifibatide (N=)	Long Tirofiban (N=)
Primary outcome, n (%)			
Yes			
No			
Death, n (%)			
Yes			
No			
Periprocedural myonecrosis (PPM), n (%)			
Yes			
No			
Urgent target vessel revascularization (uTVR), n (%)			
Yes			
No			
REPLACE-2 major bleeding, n (%)			
Yes			
No			

Note: The primary outcome is the composite of death, PPM, uTVR or REPLACE-2 major bleeding within 48 hours following PCI or hospital discharge, whichever comes first.

Note: This table will also be repeated for Per-Protocol Population.

Table 15. Bivariate Logistic Regression Model for Primary Outcome – mITT Population

Parameter	Level	Estimate	Standard Error (SE)	Odds Ratio (OR)	95% CI for OR	Risk (Proportion Difference)	Standard Error (SE) of Risk Difference	95% CI for Risk Difference	p-value *
Primary composite outcome	Short Tirofiban vs. Eptifibatide								
Primary composite outcome	Short Tirofiban vs. Long Tirofiban								
Primary composite outcome	Long Tirofiban vs. Eptifibatide								

* p-value is the overall p-value from the logistic regression model.

Note: The primary outcome is the composite of death, PPM, uTVR or REPLACE-2 major bleeding within 48 hours following PCI or hospital discharge, whichever comes first.

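### SAP Table 13 codes every stented patient as multivessel, so the covariate named as vessels treated is really a stent yes/no flag

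*SAP*

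**What the plan says.** SAP section 3.10.4 names the covariate as "Number of vessels treated (multivessel vs. single vessel" and lists "Number of stents implanted" as a separate candidate. The note under Table 15(a) repeats both. Protocol section 9.3.4 also keeps them apart: "Number of vessels treated" is an item of its own, next to items for stent count, single vessel and multivessel.

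In mock Table 13 the row is headed "Vessel involvement, n (%) ²", and its footnote gives the derivation: "Ascertained by 'Number if stents implanted' indicated on the Procedure Report Form; ≥ 1 implanted stent = multivessel". The operative part, after the ≥ sign, is "1 implanted stent = multivessel". Neither document gives any other derivation of multivessel.

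On the role of these covariates, SAP section 3.10.4 describes the work as exploratory and says that "appropriate univariate statistics will be used to identify potential confounders for inclusion in multivariable regression models".

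On data capture the protocol is not uniform. Section 5.2.3 says: "The number and position of coronary stents placed as well as the outcome of the procedure will be recorded". Section 6.0, which names the CRF, lists how many stents, their type and their length, but not their position.

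**The concern.** Vessels treated and stents implanted are different quantities. One stent can lie in only one vessel, several stents can lie in the same vessel, and a vessel can be treated with no stent. The footnote replaces the first quantity with a dichotomy of the second, cut at zero.

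This touches two outputs. Table 13 would report vessel involvement by arm under a label that does not match its content, in the mITT population and again in the per-protocol population. The same variable is a candidate for the multivariable models in Table 15(a), where 2-way interactions are also considered. An analyst who selected it would believe that the model had been adjusted for the number of vessels treated, when it had been adjusted for whether any stent was placed.

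**Working it through.** The plan states no figure here to reproduce, so the check is logical: apply the footnote to each possible patient and compare the result with the covariate as named.

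**Inputs**
- Rule: stent count ≥ 1 gives multivessel (SAP Table 13, footnote 2). The footnote does not define single vessel, so I read it as the remainder, a stent count of 0.
- Covariate as named: vessels treated, single or multivessel (SAP section 3.10.4, Table 15(a)).
- A stent count of 0 is possible: balloon angioplasty, laser atherectomy and similar procedures are eligible (protocol section 4.1, SAP section 2.7.1).
- Stenting is expected in most patients: the rationale describes planned stent placement (protocol section 1.5, SAP section 2.2).
- Planned enrolment is about 550 (SAP section 2.4).

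**Step 1. Classify each case** under the printed rule and under a cut at more than one stent.

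| Stents | Vessels treated | True class | Rule ≥ 1 | Rule > 1 |
|---|---|---|---|---|
| 0 | 1 | single | single | single |
| 0 | 2+ | multi | single (wrong) | single (wrong) |
| 1 | 1 | single | multi (wrong) | single |
| 1 | 2+ (others unstented) | multi | multi | single (wrong) |
| 2+ | 1 | single | multi (wrong) | multi (wrong) |
| 2+ | 2+ | multi | multi | multi |

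Under the printed rule, both rows with a stent and one treated vessel are wrong, so 100% of stented single-vessel patients are misclassified. The error also runs the other way: an unstented patient treated in two vessels is called single vessel. A cut at more than one stent corrects the case of one stent in one vessel. It leaves two of the printed rule's errors in place and adds one.

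**Step 2. Relation to the other covariate.** The coded variable is 1 if the stent count is at least 1, and 0 otherwise. Once the stent count is known, the flag is known. It is not a linear copy of the count, so both could be fitted together, but the flag would then carry only the contrast between some stents and none.

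**Step 3. Scale.** The documents give no stenting rate, so the range of 90% to 99% is an assumption. Unstented patients = 550 × (1 − rate):
- at 90%: 550 × 0.10 = 55
- at 99%: 550 × 0.01 = 5.5, about 6

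These counts are over all three arms together.

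**Step 4. Reach.** SAP section 3.10.1 fits the primary comparison with treatment group as the only independent factor. The vessel variable does not enter it. The variable is one of 18 candidates in section 3.10.4 and reaches a model only if univariate screening selects it.

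**The case against.** Four points can be made for the plan.

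1. *It may be a typing slip.* The same footnote has a slip in the name of the form field, and ≥ 1 may have been meant as > 1. That is plausible and worth asking. It would not repair the rule, because two stents can lie in one vessel and two vessels can be treated with fewer than two stents.
2. *It is exploratory.* This stands. A reader might infer that the non-inferiority conclusion is at risk because the adjusted models concern the primary endpoint. The documents do not support that: the deciding comparison contains no covariates.
3. *The variable is not meaningless.* This also stands. A reader might call the covariate meaningless or constant. Unstented PCI is eligible, so it can vary, and it is a valid indicator of stent use under the wrong label. The stent count remains a candidate, so some of the extent of the procedure is still captured.
4. *Stent count may have been the only field available.* The footnote points to a stent-count field on the Procedure Report Form, which is not among the documents. A reader might infer from protocol section 5.2.3 that vessel data are already in hand and that the repair is a few lines of code. Section 6.0 omits position from what goes on the CRF, and stent position cannot show a vessel treated without a stent. The availability of vessel data is therefore not established.

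**Conclusion.** The rule as printed does not measure what its label says. It produces a stent yes/no flag, misclassifies every stented patient treated in one vessel, and misclassifies unstented patients treated in more than one. On the assumed stenting range the single-vessel group would be about 10% of patients or fewer.

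The consequence is confined to one mislabelled descriptive row in Table 13 and one mislabelled candidate in the exploratory covariate models. The primary non-inferiority test is untouched. Two readings underlie this: that single vessel means a stent count of 0, and that the footnote's derivation also serves section 3.10.4 and Table 15(a), which give none of their own. How far any adjusted estimate would move cannot be worked out from the documents.

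**What to change.** First establish whether the database identifies the vessels treated at the index PCI, including those treated without a stent, and reconcile protocol sections 5.2.3 and 6.0 on whether stent position was captured.

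- **If treated-vessel data exist:** replace footnote 2 with a rule that multivessel means two or more distinct coronary vessels treated at the index PCI, and single vessel otherwise. Use the same definition in SAP section 3.10.4 and Table 15(a). Stent position alone is not enough; vessels treated without a stent need another source.
- **If they do not exist:** relabel the variable as any stent versus none, or remove it from Table 13 and from the covariate lists. Keep the stent count as a candidate either way.
- **Do not simply change the threshold** to more than one stent and keep the label.

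The first option costs a footnote, a matching line in two places and a short derivation, provided the data are there. The second needs no new data, only wording changes to the SAP. Neither affects the sample size, the primary analysis or the non-inferiority margin.

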Physician-directed standard background therapies will include dual oral antiplatelet therapy with aspirin and an approved oral P2Y₁₂ antagonist as well as antithrombotic therapy with unfractionated heparin. Physician-directed P2Y₁₂ antagonist therapy and choice of femoral or radial access site must be pre-specified prior to randomization.

The first 159 patients were randomized to the following two treatment arms on a 1:1 basis:

1. Tirofiban (25 µg/kg bolus followed by a 0.15 µg/kg/min infusion for the duration of the PCI procedure plus a minimum of one hour and up to a maximum of two hours post-PCI).
2. Eptifibatide (180 µg/kg bolus followed by a 2.0 µg/kg/min infusion for 18 hours post-PCI [minimum 12 hours mandated], with a second 180 µg/kg bolus 10 min after the first).

The three treatment arms for enrollment after the 159th patient were:

1. Short Tirofiban (25 µg/kg bolus followed by a 0.15 µg/kg/min infusion for the duration of the PCI procedure plus a minimum of one hour and up to a maximum of two hours post-PCI).
2. Eptifibatide (180 µg/kg bolus followed by a 2.0 µg/kg/min infusion for 18 hours post-PCI [minimum 12 hours mandated], with a second 180 µg/kg bolus 10 min after the first).
3. Long Tirofiban (25 µg/kg bolus followed by a 0.15 µg/kg/min infusion for 18 hours post-PCI) [minimum 12 hours mandated].

Enrolment in the Long Tirofiban arm has been completed. Enrolment continues in the Short Tirofiban and Eptifibatide arms as outlined above.

SAMPLE SIZE: Approximately 550 patients will be enrolled in the trial. The rate of the primary composite endpoint is assumed to be 51% in both the eptifibatide and tirofiban treatment groups. The absolute margin for the difference between the eptifibatide and the short tirofiban group is set at 19.1%. A sample size of approximately 500 for the comparison between the short tirofiban and the eptifibatide group was obtained by setting a power at 99% and a 1-sided alpha at 0.025. For the second test, a sample size of approximately 350 for the comparison between the short tirofiban and the long tirofiban group was obtained by setting power at 94.5% and a 1-sided alpha at 0.025. For the third test, a sample size of approximately 350 for the comparison between the long tirofiban and the eptifibatide group was obtained by setting power at 94.5% and a 1-sided alpha at 0.025.

DOSAGE/DOSAGE FORM, ROUTE, AND DOSE REGIMEN

Aspirin:	As per local practice and physician discretion

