3 STATISTICAL METHODS

3.1 Statistical Handling Policy

3.1.1 Analysis Conventions

This section details general guidelines to be used for the statistical analyses. Deviations from these general policies may be given in the specific detailed sections of this statistical analysis plan. When this situation occurs, the rules set forth in the specific section take precedence over the general conventions. The following policies will be applied to all data presentations and analyses:

- Two-tailed tests will be performed for analyses that use statistical testing with a significance level of $\alpha = 0.05$. One-tailed tests will be performed for analyses with a significance level of $\alpha = 0.025$, if applicable.
- Summary descriptive statistics will consist of the number and percentage of responses in each category for discrete variables, and the mean, median, standard deviation (SD), minimum, maximum, and 95% confidence interval for continuous variables.
- All mean and median values will be formatted to one decimal place. Standard deviation values will be formatted to two decimal places.
- All percentages will be rounded to one decimal place. Where appropriate, the number and percentage of responses will be presented in the form XX (XX.X %), where the percentage is in the parentheses.
- For any analysis output, estimates and their corresponding standard deviations and/or standard errors will be reported up to the 3rd or 4th decimal place, per the default output of SAS.
- All p-values will be rounded to 4 decimal places (SAS format p-value). All p-values that round to 0.000 will be presented as '<0.001' and p-values that round to 1.000 will be presented as '>0.999'. Any p-value ≤ 0.05 will be considered statistically significant.
- All listings will be sorted for presentation in order of treatment group, site number, subject number, and date of procedure or event, when applicable.

- When necessary for analysis purposes, partial dates will be imputed (i.e., turned into complete dates) using the most conservative approach.
- Where appropriate, all analyses and summary tables will have the population sample size for each treatment group in the column heading.
- Tables will include titles with the corresponding analysis population and footnotes describing the analyses involved, and listings of covariates included in the analyses, where relevant.
- Version 20.0 (or higher) of MedDRA will be used for adverse event and pre-treatment conditions coding.

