3.10 Analysis of the Study Endpoints

3.10.1 Analysis of the Primary Endpoint

To evaluate the effectiveness of tirofiban versus eptifibatide, we look at the proportion of patients with at least one of the following endpoint measurements: death, PPM, uTVR or REPLACE-2 Major bleeding within 48 hours following PCI or hospital discharge, whichever comes first. For each pairwise comparison:

- The short tirofiban group is non-inferior to the eptifibatide group;
- The short tirofiban group is non-inferior to the long tirofiban group;
- The long tirofiban group is non-inferior to the eptifibatide group;

The following hypothesis will be tested:

$$H_0: C - T \leq -0.191$$

$$H_1: C - T > -0.191$$

To test this hypothesis, the difference ($C - T$) and its associated one-sided 97.5% confidence interval will be calculated. If the lower bound of the interval is greater than -0.191, the non-inferiority will be claimed. In order to compute the risk (proportion) difference for data with binary

response (“Yes” vs. “No”), a bivariate logistic regression will be performed for each pairwise comparison with the following specifications:

- The dependent variable will be “composite endpoint” and the independent factor will be “treatment group”;
- The risk (proportion) difference between two methods as well as its confidence interval will be estimated;
- The non-inferiority margin is 19.1%

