Note: This table will also be repeated for Per-Protocol Population.

Table 15 (a) Multivariate Logistic Regression Models for Primary Outcome – mITT Population

Parameter	Level	Estimate	Standard Error (SE)	Odds Ratio (OR)	95% CI for OR	Risk (Proportion Difference)	Standard Error (SE) of Risk Difference	95% CI for Risk Difference	p-value *
Primary composite outcome	Short Tirofiban vs. Eptifibatide								
Primary composite outcome	Short Tirofiban vs. Long Tirofiban								
Primary composite outcome	Long Tirofiban vs. Eptifibatide								

* p-value is the overall p-value from the logistic regression model.

Note: The following potential covariates, as well as all significant 2-way interaction terms, will be assessed using appropriate univariate statistics for consideration in the multivariate regression models:

- *Patient with acute coronary syndrome*
- *STEMI > 48 hours*
- *Stable angina*
- *Baseline troponin (positive vs. negative)*
- *Planned PCI access (femoral vs. radial)*
- *Number of stents implanted*
- *Number of vessels treated (multivessel vs. single vessel)*
- *Total infusion time*
- *Patients receiving P2Y12 antagonist therapy between 24 and 6 hours prior to randomization*
- *Patients receiving P2Y12 antagonist therapy between 6 and 1 hours prior to randomization*
- *Patients receiving P2Y12 antagonist therapy between 1 hour prior to randomization and 15 minutes after completion of the PCI procedure*
- *Type 2 diabetes mellitus*
- *Age < 65 years, ≥ 65- 74 years and ≥ 75 years*

- *Sex*
- *Clopidogrel*
- *Prasugrel*
- *Ticagrelor*
- *Indication for PCI (Urgent vs. Elective)*

Note: This table will also be repeated for Per-Protocol Population.

Table 16. Descriptive Statistics of Secondary Outcomes by Treatment Group – mITT Population

Parameter	Treatment Group		
	Short Tirofiban (N=)	Short Tirofiban (N=)	Short Tirofiban (N=)
Secondary outcome 1, n (%)			
Yes			
No			
Secondary outcome 2, n (%)			
Yes			
No			
Secondary outcome 3, n (%)			
Yes			
No			
Secondary outcome 4, n (%)			
Yes			
No			
Secondary outcome 5, n (%)			
Yes			
No			
Secondary outcome 6, n (%)			
Yes			
No			
Secondary outcome 7, n (%)			
Yes			
No			

Parameter	Treatment Group		
	Short Tirofiban (N=)	Short Tirofiban (N=)	Short Tirofiban (N=)
Secondary outcome 8, n (%)			
Yes			
No			

Note: The definitions of secondary outcomes are:

- *Secondary outcome 1: death, PPM or uTVR within 48 hours following PCI or hospital discharge, whichever comes first*

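### The p-value in SAP Tables 15, 15(a) and 17 is the overall logistic-model p-value: it does not test the non-inferiority null, and in the exploratory adjusted Table 15(a) it does not isolate treatment

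*SAP*

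**What the plan says.** SAP 3.10.1 sets the null as C - T at or below -0.191 for each of the three pairwise comparisons, and decides from a one-sided 97.5% confidence interval: "If the lower bound of the interval is greater than -0.191, the non-inferiority will be claimed". To obtain the risk difference, "a bivariate logistic regression will be performed for each pairwise comparison with the following specifications"; the specifications make treatment group the only independent factor.

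The results shells are in SAP Section 6. Table 15 (primary outcome), Table 15(a) (adjusted models for the primary outcome) and Table 17 (secondary outcomes) each show the odds ratio, the risk difference with its standard error and 95% CI, and one p-value. All three carry the footnote "p-value is the overall p-value from the logistic regression model". No p-value against a margin is defined anywhere.

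For Table 15(a) a note adds: "The following potential covariates, as well as all significant 2-way interaction terms, will be assessed using appropriate univariate statistics". Eighteen candidate covariates follow. SAP 3.10.4 calls this covariate modelling exploratory.

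SAP 3.1.1 has the general convention "Any p-value ≤ 0.05 will be considered statistically significant". The same section assigns a level of 0.025 to one-tailed tests and lets specific sections override the general rules.

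**The concern.** The p-value stands in the same row as the non-inferiority comparison but answers another question. In Tables 15 and 17 it tests an odds ratio of 1. A clearly non-inferior result would then carry a large p-value, and a failed one a small p-value.

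In Table 15(a) the overall test covers every coefficient in the model. A row labelled with a treatment comparison could show p at or below 0.05 because of a prognostic covariate alone. The candidates include baseline troponin, and the composite is partly defined by troponin, so a prognostic covariate is plausible.

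The shells also do not say in which order the risk difference is subtracted, although the rule in 3.10.1 works only for C - T. What is at stake is a misreading of the main results tables in the mITT and per-protocol versions, not the formal decision.

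**Working it through.** **Inputs from the documents.** Event rate 51% in both arms, about 500 patients for short tirofiban versus eptifibatide and about 350 for each co-primary comparison, margin 0.191, and "setting a power at 99% and a 1-sided alpha at 0.025" for the first test (Protocol Synopsis; SAP 2.6 and 3.10.1). 1:1 allocation gives 250 per arm for the first test.

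**The plan's own figures.** With n per arm = (z_alpha + z_beta)² × 2p(1 - p) / margin²:

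- First test, 99% power: (1.960 + 2.326)² × 2 × 0.51 × 0.49 / 0.191² = 251.7, so 252 per arm, 504 in total (plan: about 500).
- Co-primary tests, 94.5% power: 174 per arm, 348 in total (plan: about 350).
- Outcomes at 10 times the upper limit (32%, margin 12.4 points, 85% power): 255 per arm, 510 in total (plan: about 500).

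The sample sizes reproduce and are not in dispute.

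**Tables 15 and 17: two different tests on the same data.** Take 250 per arm, C = 0.51 and a range of assumed observed tirofiban rates T.

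- Printed p: two-sided Wald test of ln[T/(1 - T)] - ln[C/(1 - C)], with SE = sqrt[1/(250T) + 1/(250(1 - T)) + 1/(250C) + 1/(250(1 - C))].
- Non-inferiority p: one-sided, z = (C - T + 0.191)/SE, with SE = sqrt[C(1 - C)/250 + T(1 - T)/250].

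| T | C - T | Lower 97.5% bound | Non-inferiority p | Claimed? | Printed p |
|---|---|---|---|---|---|
| 51% | 0.00 | -0.088 | 0.00001 | yes | 1.00 |
| 55% | -0.04 | -0.127 | 0.0004 | yes | 0.37 |
| 60% | -0.09 | -0.177 | 0.011 | yes | 0.043 |
| 63% | -0.12 | -0.206 | 0.053 | no | 0.007 |

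Example, T = 60%: SE of the difference = 0.0443, z = (-0.09 + 0.191)/0.0443 = 2.28, p = 0.011. Log odds ratio 0.365, SE 0.181, z = 2.02, p = 0.043.

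Whole-number counts around the decision boundary, using the overall likelihood-ratio p, agree. With 128/250 on control, 154/250 on tirofiban gives a bound of -0.1905 (just claimed), non-inferiority p 0.024 and overall p 0.019. One more event, 155/250, gives -0.194 (not claimed), 0.030 and 0.015. The printed p does not register the change of decision.

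With true rates exactly at the margin (51% and 70.1%), SE = 0.0429 and 0.191/0.0429 - 1.96 = 2.50, so the zero-difference p is at or below 0.05 in about 99% of trials. The non-inferiority test rejects in 2.5%.

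**Table 15(a): joint test.** Simulation with 1,000 trials per row, 250 per arm, no treatment effect, and one binary covariate at 50% prevalence. Prevalence and covariate effects are assumptions; the documents give none.

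| Covariate risk difference | Overall p ≤ 0.05 | Treatment-term p ≤ 0.05 |
|---|---|---|
| 10 points | 52% | 5% |
| 20 points | 99% | 5% |
| 30 points | 100% | 4% |

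**Direction of the difference.** At T = 63% the C - T interval runs from -0.206 to -0.034, so the rule fails. If the table printed T - C, the interval would be +0.034 to +0.206. Its lower limit exceeds -0.191, so applying the rule to it unchanged would give the wrong answer. The correct check there would be the upper limit against +0.191.

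**The case against.** The strongest reply is that no decision uses this p-value. SAP 3.10.1 decides from the confidence bound, Protocol 9.6 also assigns non-inferiority to confidence intervals, and Table 15 already prints a 95% CI whose relevant limit equals the one-sided 97.5% bound. In every scenario above that interval gives the right answer. This stands, and it limits the point to reporting.

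Second, the zero-difference p-value is valid for what it tests and matches the odds ratio beside it. At T = 60% it usefully shows that tirofiban is worse although non-inferiority is met. This stands too: it is a reason to relabel the p-value rather than to require its removal.

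Third, Table 15(a) is exploratory. That lowers the stakes but does not make a joint-model p-value right for a row named after a treatment comparison.

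Three stronger readings are tempting, and the documents do not support them:

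- A reader might infer that the p-value in Table 15(a) does not test treatment at all. Treatment is one term in the joint test; if no covariate were selected, the test would reduce to the treatment test of zero difference.
- A reader might infer that the tables reverse the sign of the rule. The row labels name tirofiban first but do not define the subtraction, and 3.10.1 says C - T. The direction is unlabelled, not shown to be reversed.
- A reader might infer that the 0.05 convention contradicts the one-sided 0.025 level. SAP 3.1.1 provides for 0.025 in one-tailed tests and lets specific sections take precedence.

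**Conclusion.** The point holds as a reporting defect. In Tables 15 and 17 the only p-value tests zero difference. Over the range examined it falls as tirofiban worsens while the non-inferiority p rises: 1.00 against 0.00001 for equal arms, 0.007 against 0.053 at 63% versus 51%. In Table 15(a) the p-value does not isolate treatment and can be at or below 0.05 because of a covariate alone, in about 52% to 100% of null-treatment trials for assumed covariate effects of 10 to 30 points.

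The non-inferiority conclusion does not change if SAP 3.10.1 is followed. The figures for Tables 15 and 17 assume 250 per arm, 51% on control and the normal approximation; the tirofiban rates above 51% are illustrations, since the plan assumes equal rates. The size of the Table 15(a) problem depends on which covariates are selected and how prognostic they are.

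**What to change.** - **Table 15(a):** replace the overall model p-value with the test of the treatment term, reported with the adjusted risk difference and its interval.
- **Tables 15 and 17:** add the one-sided p-value for the null C - T at or below minus the margin, from the risk difference and its standard error, judged at 0.025. The margin is 0.191 for the primary outcome, and 0.124 for the two outcomes at 10 times the upper limit in short tirofiban versus eptifibatide. Label the existing p-value as a two-sided test of no difference, or drop it.
- **All three tables:** label the risk difference as C - T. In Tables 15 and 17, mark the lower 97.5% bound as the limit to compare with minus the margin.

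This costs edits to three table shells and their footnotes and a few lines of code. It needs no new data and leaves the decision rule and the sample size unchanged.
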